### **Pneumonitis**

Pneumonitis has been reported in association with use of anti-PD-L1/anti-PD-1 antibodies (Brahmer et al 2012). It is also seen in 5% to 15% of patients irradiated for breast, lung, and mediastinal tumours. The risk of developing radiation pneumonitis is directly related to the volume of irradiated lung, the amount of radiation given, and the use of concurrent chemotherapy. Additional risk factors include co-morbid lung disease, poor baseline pulmonary function testing, and low performance status.

## **Radiation pneumonitis**

Symptoms of radiation pneumonitis, including low-grade fever, congestion, dry cough, pleuritic chest pain, and a sensation of chest fullness, usually develop 1 to 3 months after completion of radiation therapy. Diagnosis is difficult, often complicated by co-morbid conditions and radiation injury to adjacent structures (eg, oesophagus, pericardium). Prednisone, in dosages of at least 50 to 60 mg per day for 1 week followed by an extended taper, has been shown to abate symptoms and improve lung function. Bronchodilators and supplemental oxygen may be necessary.

More specific guidelines for the evaluation and treatment of pneumonitis are described in detail in the TMGs.

### **5.5.4 Additional study drug**

No additional study drug is required in this study.

### **5.5.5 Labelling**

Labels will be prepared in accordance with Good Manufacturing Practice (GMP) and local regulatory guidelines. The labels will fulfil GMP Annex 13 requirements for labelling. Label text will be translated into local language.

The label will include the following information:

- Name of sponsor (AstraZeneca)
- Study drug dosage form, route of administration, and quantity of dosage units
- Storage conditions
- Study code
- Enrolment code
- Directions for use
- The name of the Principal Investigator, where applicable (this may be pre-printed or added on the label when the study drug is dispensed)
- The period of use eg, expiry date.
- Product Lot Identifier
- Medication Identity Number
- For clinical study use only.

Labels will be provided as either a single panel label or as multi-language booklet labels.

### **5.5.6 Storage**

All study drugs should be kept in a secure place under appropriate storage conditions and may only be dispensed by a pharmacist or a qualified designee. The investigational product label on the kit specifies the appropriate storage. MEDI4736 must be stored at 2°C to 8°C.

## **5.6 Concomitant and post-study treatment(s)**

Investigators may prescribe concomitant medications or treatments (eg, acetaminophen, diphenhydramine) deemed necessary to provide adequate prophylactic or supportive care except for those medications identified as “excluded” as listed below:

- Any investigational anticancer therapy
- Any concurrent chemotherapy, radiotherapy, immunotherapy, biologic, or hormonal therapy for cancer treatment. Concurrent use of hormones for non-cancer-related conditions (eg, insulin for diabetes and hormone replacement therapy) is acceptable. NOTE: Local treatment of isolated lesions, excluding target lesions, for palliative intent is acceptable (eg, by local surgery or radiotherapy).
- Immunosuppressive medications including, but not limited to systemic corticosteroids at doses beyond 10 mg/day of prednisone or equivalent, methotrexate, azathioprine, and tumour necrosis factor alpha blockers. Use of immunosuppressive medications in patients for the management of study drug-related AEs or their use in patients with contrast allergies is acceptable. In addition, use of inhaled and intranasal corticosteroids is permitted.
- Live attenuated vaccines within 30 days of dosing. Inactivated viruses such as those in the influenza vaccine are permitted.

Other medication, which is considered necessary for the patient’s safety and well-being, may be given at the discretion of the Investigator and recorded in the appropriate sections of the eCRF.

## **5.7 Treatment compliance**

Treatment compliance will be assured by site reconciliation of medication dispensed.

The administration of all study drugs (including investigational products) should be recorded in the appropriate sections of the eCRF. The Investigator or pharmacy must retain records of all study drugs administered. The study monitor will check these records to confirm the compliance with the protocol administration schedule. Administration of durvalumab as re-treatment following the final DCO for the study will be recorded in site documents for the purpose of supply management but will not otherwise be reported.

Use of investigational product in doses in excess of that specified in the protocol is considered to be an overdose. Refer to Section 13.2 for procedures in case of overdose.

### **5.7.1 Accountability**

The study drug provided for this study will be used only as directed in the study protocol.

The study personnel will account for all study drugs dispensed to and returned from the patient.

Study site personnel will account for all study drugs received at the site, unused study drugs and for appropriate destruction. Certificates of delivery and destruction should be signed.

## **5.8 Discontinuation of investigational product**

Patients may be discontinued from investigational product in the following situations:

- Patient decision. The patient is at any time free to discontinue treatment, without prejudice to further treatment.
- Adverse Event, that in the opinion of the Investigator or the sponsor, contraindicates further dosing
- Severe non-compliance to study protocol that, in the opinion of the Investigator or sponsor, warrants withdrawal; eg, refusal to adhere to scheduled visits
- Patient is determined to have met one or more of the exclusion criteria for study participation at study entry and continuing study drug might constitute a safety risk
- Any AE that meets criteria for discontinuation, as defined in Section 5.5.3
- An AE related to study drug that is  $\geq$ Grade 3, with the exception of toxicities that do not meet criteria for discontinuation as defined Section 5.5.3
- $\geq$ Grade 3 infusion reaction
- Initiation of alternative anticancer therapy including another investigational agent
- Confirmed PD and Investigator determination that the patient is no longer benefiting from treatment
- Pregnancy or intent to become pregnant.

If the patient is discontinued from study drug, the scheduled study visits, data collection and procedures should continue according to this study protocol until study closure. Alternatively, if the patient does not agree to this option, a modified follow-up through eg, regular telephone contacts or a contact at study closure should be arranged, if agreed to by the patient and in compliance with local data privacy laws/practices. See Section 5.8.1.

Following final DCO for the study, SAEs occurring in patients on treatment or in the 90 day follow up period after the last dose of durvalumab must be reported directly to AstraZeneca

Global Patient Safety as described in Section 6.4.4. Other AEs should be managed according to the durvalumab TMGs (refer to Section 5.5.3), and will be followed up per the Investigators' judgment but will not otherwise be reported or recorded for the purposes of this study. Following the final DCO for the study, Investigators who intend to commence or continue re-treatment with durvalumab should continue to monitor patients' safety laboratory assessments so as to ensure that no laboratory abnormalities or AEs that could potentially result in IP discontinuation are overlooked. All data will be recorded into the patients' charts but will not be otherwise documented for the purposes of this study.

Withdrawal of consent for PGx and biological sampling is included in Section 7.5.

### **5.8.1 Procedures for discontinuation of a patient from investigational product**

Patients who are permanently discontinued from further receipt of study drug, regardless of the reason (withdrawal of consent, due to an AE, other), will be identified as having permanently discontinued study drug.

A patient that decides to discontinue investigational product will always be asked about the reason(s) for discontinuation and the presence of any AEs. If possible, they will be seen and assessed by an Investigator(s). Adverse events will be followed up (See Sections 6.4.3 and 6.4.4), and questionnaires returned by the patient.

If a patient is withdrawn from the study, see Section 5.9.

#### **Assessments following withdrawal of study drug**

Patients who are permanently discontinued from receiving study drug will remain in the study and will be followed per the study plans in Table 2 or Table 3 including the collection of any protocol-specified blood specimens and completion of questionnaires and case report forms (CRFs) relating to PRO and hospital resource use, unless consent is withdrawn or the patient is lost to follow-up or enrolled in another clinical study. All patients will be followed for survival up to the time of final DCO for the study, at which time, unless they remain eligible for re-treatment with durvalumab, they will be considered to have completed the study. Re-treatment will not be an available treatment option within this protocol following the final DCO for the long-term follow up phase of the study (CSP amendment 7). Patients who decline to return to the site for evaluations will be offered follow-up by phone as specified in the study plans as an alternative (Table 2 [for follow-up of patients achieving disease control or who are discontinued due to toxicity or a reason other than confirmed PD] and Table 3 [for follow-up of patients discontinuing due to confirmed PD]). However, patients who discontinue due to an AE will need to attend all protocol-specified visits and all assessments will be conducted as scheduled.

All patients who have any Grade 3 or 4 laboratory values at the time of discontinuation must have further tests performed and the results recorded on the appropriate eCRF until the laboratory values have returned to Grade 1 or 2, unless these values are not likely to improve because of the underlying disease.

At discontinuation, all on-going study-related toxicities and SAEs must be followed until resolution, unless in the Investigator's opinion, the condition is unlikely to resolve due to the patient's underlying disease.

All new AEs occurring for up to 90 days after the last dose of study drug must be recorded in the eCRF and reported as SAEs, if applicable.

Patients who have disease control following completion of 12 months of treatment or patients who are withdrawn from study drug for reasons other than confirmed PD will continue to have objective tumour assessments (see [Table 2](#)).

Drug or study procedure related SAEs must be captured until the patient completes the follow-up period following discontinuation of study drug (due to confirmed PD) or is permanently withdrawn from the study (see Section 5.9).

When confirmed PD has been documented, the long-term follow-up information for survival should be collected per [Table 3](#) (for patients discontinuing due to confirmed PD) (by telephone contact with the patient, patient's family, or by contact with the patient's current physician. An exception is any patient with confirmed PD that continues to receive study drug at the discretion of the Investigator (following consultation with the sponsor), who can receive study drug for a maximum of 12 months during the initial treatment period or for as long as the Investigator judges that they are gaining clinical benefit in the re-treatment period and will follow the assessments in [Table 1](#) including tumour assessments until study drug is discontinued (the patient must re-consent to be treated through disease progression [see Section 8.4]).

Study drug should be discontinued if there is confirmed progression of disease (PD) following a previous response (PR or CR) to study drug.

Both the patient and the physician will be asked about the subsequent treatment the patient receives during the follow-up period ([Table 2](#) [for follow-up of patients achieving disease control or who are discontinued due to toxicity or a reason other than confirmed PD] and [Table 3](#) [for follow-up of patients discontinuing due to confirmed PD]).

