#### 3.2.3.4 Rationale for study endpoints (efficacy)

The primary aim of this study is to determine the efficacy of MEDI4736 (10 mg/kg Q2W via iv infusion) compared with placebo in terms of OS and PFS. Progression free survival may serve as a surrogate endpoint for OS when differences between treatment groups are of sufficient magnitude and clinically important ([FDA Guidance 2011](#), [Pazdur 2008](#)). In certain settings, the utility of survival as an endpoint may potentially be confounded by subsequent therapies. Specifically, there are currently a number of molecules, targeting the PD-1/PD-L1 pathway, in late-stage development in second- and third-line squamous NSCLC. It is anticipated that these agents may be approved or become available for use through expanded-access mechanisms or additional clinical studies while this study is ongoing. This poses challenges in being able to fully characterize effects on OS if patients subsequently receive these immunotherapeutic agents. However, given that tumour response to immunotherapy may differ from typical responses, both PFS and OS are co-primary endpoints with the study powered for OS.

Antitumour activity will be assessed according to RECIST v1.1 guidelines, with the understanding that in the context of post-radiation changes tumour assessment may be difficult and may need to be repeated over time to reach a clear determination regarding responses and/progressive disease (see Section 6.3). The co-primary analysis of PFS will be based on programmatically derived PFS based upon BICR assessments. Sensitivity analyses will also be performed using data from site Investigators tumour data from all scans based

upon RECIST 1.1 and site Investigator tumour data from all scans based upon RECIST 1.1 modified for confirmation of progression. Exploratory analysis will also be performed for data obtained from the BICR on a subset of 250 evaluable patients scans using irRC.

This is because the response to immunotherapy may differ from typical responses observed with cytotoxic chemotherapy including the following (per [Wolchok et al 2009](#)):

1. Response to immunotherapy may be delayed
2. Response to immunotherapy may occur after PD by conventional criteria
3. SD while on immunotherapy may be durable and represent clinical benefit.

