## **5.9 Withdrawal from study**

Patients may be discontinued from the study in the following situations:

- Patient decision. The patient is at any time free to discontinue treatment, without prejudice to further treatment
- Severe non-compliance to study protocol that, in the opinion of the Investigator or sponsor, warrants withdrawal; eg, refusal to adhere to scheduled visits
- Patient lost to follow-up

Patients are at any time free to withdraw from study (investigational product and assessments), without prejudice to further treatment (withdrawal of consent). Such patients will always be asked about the reason(s) and the presence of any AEs. If possible, they will be seen and assessed by an Investigator. Adverse events will be followed up (see Sections 6.4.3 and 6.4.4); and questionnaires and all study drugs should be returned by the patient.

If consent is withdrawn, the patient will not receive any further study drug or further study observation. The patient will be specifically asked if they are withdrawing consent to:

- Further participation in the study including any further follow-up (eg, survival calls)
- Withdrawal of consent to the use of their study generated data
- Withdrawal to the use of any samples (see Section 7.5).

Note that the patient may be offered additional tests or tapering of treatment to withdrawal for safety, and will be offered follow-up by phone as specified in the study plans as an alternative (Table 2 [for follow-up of patients achieving disease control or who are discontinued due to toxicity or a reason other than confirmed PD] and Table 3 [for follow-up of patients discontinuing due to confirmed PD]). If a patient wishes to withdraw their consent to further participation in the study, including survival follow-up (by phone) this should be clearly documented in the patient notes and in the clinical study database.

Patients will be considered lost to follow-up only if no contact has been established by the time the study is completed such that there is insufficient information to determine the patient's status at that time.

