Administration of study drug will continue between the initial assessment of progression and confirmation for progression. For all patients who are treated through progression and patients who achieve disease control and restart study drug upon evidence of PD (according to RECIST 1.1) during follow-up, the Investigator should ensure patients do not have any significant, unacceptable or irreversible toxicities that indicate continuing treatment will not further benefit the patient. The patient must continue to meet those inclusion and exclusion criteria that are relevant to treatment through disease progression and re-treatment as specified in Section 4.3. Patients with rapid tumour progression or with symptomatic progression that requires urgent medical intervention (eg, central nervous system metastasis, respiratory failure due to tumour compression, spinal cord compression) will not be eligible to continue to receive study drug.

Progression would be considered confirmed if the following criteria are met:

- $\geq 20\%$  increase in the sum diameters of target lesions compared with the nadir at 2 consecutive visits with an absolute increase of at least 5 mm

The assessment of progression of  $\geq 20\%$  increase in the sum diameters of target lesions compared with the nadir is at the first progression time point relative to the nadir (the smallest sum of diameters and this may be at baseline or subsequent follow-up visit). The confirmed scan confirms the persistence of the  $\geq 20\%$  increase relative to the nadir

- and/or significant progression (worsening) of non-target lesions or new lesions at the confirmatory PD time-point compared with the first time point where progression of non-target lesions or new lesions identified
- and/or additional new unequivocal lesions at the confirmatory PD time-point compared with the first time point new lesions identified.

In the absence of clinically significant deterioration the Investigator should continue the patient on study drug until progression is confirmed.

If progression is not confirmed, then the patient should continue study drug and on treatment assessments.

If a patient discontinues study drug (and/or receives a subsequent cancer therapy) prior to progression then the patient should still continue to be followed until confirmed objective disease progression.

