#### 6.4.9 Other safety assessments

Pregnancy tests on either blood (serum  $\beta$ -hCG) or urine (hCG) samples will be performed for pre-menopausal women of childbearing potential at the times specified in [Table 1](#). Tests will be performed by the hospital's local laboratory. If results are positive the patient is ineligible/must be discontinued from the study. In the event of a suspected pregnancy during the study, the test should be repeated.

Other safety tests to be performed at Screening include:

- Coagulation tests: prothrombin time, APTT and INR only performed at Screening and if clinically indicated
- Hepatitis B and C testing as per local practice
- HIV-1 antibody testing as per local practice
- T3 free (if available), total T4 (or T4 free), and TSH.

Timings for additional thyroid function tests (TSH and T3 free [if available] and total T4 [or T4 free]) are shown in [Table 1](#) (Screening and the Treatment Period), [Table 2](#) (for follow-up of patients achieving disease control or who are discontinued due to toxicity or a reason other than confirmed PD) and [Table 3](#) (for follow-up of patients discontinuing due to confirmed PD).

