##### **11.1.3.2 Progression free survival**

PFS (per RECIST 1.1 as assessed by the BICR) will be defined as the time from the date of randomisation until the date of objective disease progression or death (by any cause in the absence of progression) regardless of whether the patient withdraws from randomised therapy or receives another anti-cancer therapy prior to progression. Patients who have not progressed or died at the time of analysis will be censored at the time of the latest date of assessment from their last evaluable RECIST 1.1 assessment. However, if the patient progresses or dies after

2 or more missed visits, the patient will be censored at the time of the latest evaluable RECIST 1.1 assessment prior to the 2 missed visits. If the patient has no evaluable visits or does not have baseline data they will be censored at Day 1 unless they die within 2 visits of baseline.

The PFS time will always be derived based on scan/assessment dates not visit dates.

RECIST 1.1 assessments/scans contributing towards a particular visit may be performed on different dates. The following rules will be applied:

- The date of progression will be determined based on the earliest of the scan dates of the component that triggered the progression for the adjudicated reviewer selecting PD or of either reviewer where both select PD as a time point response and there is no adjudication for central review (BICR) data
- For investigational assessments, the date of progression will be determined based on the earliest of the RECIST assessment/scan dates of the component that indicates progression
- When censoring a patient for PFS the patient will be censored at the latest of the dates contributing to a particular overall visit assessment.

**Note:** For target lesions, only the latest scan date is recorded in the RECIST eCRF out of all scans performed at that assessment for the target lesions and similarly for non-target lesions only the latest scan date is recorded out of all scans performed at that assessment for the non-target lesions.

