### **12.3 Determination of sample size**

The sample size for this study was selected to be consistent with the research hypothesis as described in Section 1.2.

The two co-primary endpoints of this study are OS and PFS. To control for type-I error, a significance level of 2.5% will be used for analysis of OS and a significance level of 2.5% will be used for analysis of PFS. The study will be considered positive (a success) if either the PFS analysis results and/or the OS analysis results are statistically significant.

Approximately 702 patients will be randomised 2:1 to obtain 491 death events in the ITT population (70% maturity). The primary PFS analysis DCO will occur when it is expected that 458 PFS events have occurred (65% maturity). If the true PFS HR is 0.67, the study will provide at least 95% power to demonstrate a statistically significant difference for PFS with a 2-sided significance level of 2.5% in the ITT population; this translates to a 5-month benefit in median PFS over 10 months on placebo if PFS is exponentially distributed. The smallest treatment difference that would be statistically significant is a HR of 0.8. A recruitment period of approximately 22 months and a follow-up period of 14 months are expected for the PFS endpoint. Therefore it is anticipated that this PFS analysis could be performed approximately 36 months after the first patient has been randomised.

The primary OS analysis DCO will occur when it is expected that 491 OS events have occurred (70% maturity). If the true OS HR is 0.73, this number of death events will provide at least 85% power to demonstrate a statistically significant difference for OS, assuming a 2.5% 2-sided significance level in the ITT population; this translates to an 8-month benefit in median OS over 22 months on placebo if OS is exponentially distributed. The smallest treatment difference that would be statistically significant is a HR of 0.81. A recruitment period of approximately 22 months and a follow-up period of 40 months are expected for the OS endpoint. Therefore it is anticipated that this OS analysis could be performed at approximately 62 months after the first patient has been randomised.

Please refer to [Appendix D](#) for information on PGx.

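### Protocol Section 5.8.1 makes off-drug follow-up conditional on not joining another trial, which contradicts Sections 5.8 and 6.3 and the PFS definition on whether scans continue

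*Protocol*

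**What the plan says.** Protocol Section 5.8.1 (Assessments following withdrawal of study drug) keeps patients who permanently stop drug on the Table 2 or Table 3 plan "unless consent is withdrawn or the patient is lost to follow-up or enrolled in another clinical study". Those tables hold the tumour scans, questionnaires and subsequent-therapy records and, in Table 3, the second-progression checks. The next sentence keeps all patients in survival follow-up, with no such exception.

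Other places point the other way:

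- **Section 5.8** lists starting another anti-cancer or investigational agent as a ground for stopping drug. It then says that "the scheduled study visits, data collection and procedures should continue according to this study protocol until study closure".
- **Section 6.3** requires scans until confirmed progression, whatever the reason for stopping drug and whatever therapy follows. If a patient stops drug or starts another cancer therapy before progression, "then the patient should still continue to be followed until confirmed objective disease progression".
- **Section 5.8.1, later paragraphs**, tell patients who stop for an adverse event to attend every visit and assessment. Patients off drug without confirmed progression are to go on having tumour assessments.
- **Protocol Section 11.1.3.2 and SAP Section 3.2.1.2** count PFS events "regardless of whether the patient withdraws from randomised therapy or receives another anti-cancer therapy prior to progression".

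A second mismatch concerns pregnancy tests. Section 6.4.9 says "If results are positive the patient is ineligible/must be discontinued from the study", whereas Sections 5.8 and 13.3.1 speak only of discontinuing the investigational product.

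**The concern.** The PFS definition follows a treatment-policy approach: progression or death counts even after drug has stopped and other therapy has begun. That works only if scans continue. The 5.8.1 exception puts joining another trial on the same footing as withdrawing consent, so a site could properly stop scanning a patient whom 6.3 tells it to scan.

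Entry into other trials is foreseeable. Section 3.2.3.4 expects agents on the same pathway to "become available for use through expanded-access mechanisms or additional clinical studies while this study is ongoing". SAP Section 4.2.1.1 plans to tabulate patients who enter an immunotherapy trial. The decision to join another trial may be related to how the patient is doing, so censoring at that point may be informative for a co-primary endpoint. How it is handled would depend on which sentence a site reads.

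**Working it through.** **1. Who is affected.** For co-primary PFS the patient must be off study drug, have no BICR progression, have no site-confirmed progression, and join another trial. Patients with an earlier BICR progression already have their event, because SAP 3.2.1.2 uses the first objective progression and asks for confirmation only in a sensitivity analysis. After site-confirmed progression and drug discontinuation, Table 3 makes scans optional and ends them at a new treatment, so the exception changes little for their scans. Second-progression checks sit in Table 3, so for PFS2 the exception also reaches patients who join another trial after first progression.

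**2. What happens to their PFS time.** SAP 3.2.1.2 censors at the last RECIST assessment. A progression or death after two or more missed visits is not counted. The gap is 18, 22 or 26 weeks, depending on when the last assessment fell. A death soon after leaving the scan schedule still counts for PFS; a later death counts for OS only.

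**3. Whether the planned sensitivity analysis repairs it.** The attrition analysis in SAP 4.2.1.2 restores events that followed missed assessments, but it also censors patients at their last assessment before subsequent therapy. A patient treated in another trial is therefore censored again. The reversed-censoring plot and the by-arm count of premature censoring would show a differential loss. Neither recovers a scan that was never taken.

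**4. The design figure.** Section 12.3 says "the study will provide at least 95% power to demonstrate a statistically significant difference for PFS with a 2-sided significance level of 2.5" per cent, for a true HR of 0.67 and 458 events with 2:1 allocation.

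- Power = Φ(|ln HR| × √(d × 1/3 × 2/3) − z), with z = 2.241 for two-sided 2.5%.
- √(458 × 2/9) = 10.09 and |ln 0.67| = 0.4005, so power = Φ(4.040 − 2.241) = 96.4%.
- Critical HR = exp(−2.241/10.09) = 0.80.

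Both agree with the stated figures.

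**5. Events lost and not replaced (assumed rates).** With d = 458 × (1 − f) in the same formula:

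- f = 2%: 448.8 events, power 96.1%
- f = 5%: 435.1 events, power 95.5%
- f = 10%: 412.2 events, power 94.4%
- f = 15%: 389.3 events, power 93.1%

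Power of 95% needs 424 events, so (458 − 424)/458 = 7.4% could be lost before power fell below the stated figure. In practice the cut-off waits for 458 events, so the main cost is time rather than power.

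**6. Direction of any bias.** Suppose a fraction f of would-be events in an arm is censored just before the event. The observed hazard in that arm is multiplied by (1 − f), so observed HR = 0.67 × (1 − f_MEDI4736)/(1 − f_placebo). Equal fractions cancel and leave 0.67. As an illustration of sign only, 5% in placebo alone gives 0.67/0.95 = 0.705, and 5% in MEDI4736 alone gives 0.67 × 0.95 = 0.637. Censoring every affected patient just before the event in one arm only is an extreme assumption, and no such rates are in the documents.

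**The case against.** The strongest reply is that the exception is an outlier in otherwise consistent text. Section 5.8, Section 6.3 and later sentences of 5.8.1 all require visits or scans to continue, and they cover the obvious cases: patients who stop for toxicity and patients who complete 12 months. This stands. A reader might infer from the exception that follow-up ends, or that scans certainly stop before progression. The documents do not support that: survival follow-up continues for everyone, and several passages tell sites to go on scanning. What remains is a contradiction, since no passage says which instruction prevails.

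A reader might also infer a material shift in the PFS hazard ratio. That is not supported either. No rate is given, the trial is double-blind so loss may be similar in both arms, and Section 3.2.3.4 concerns agents in later-line disease and confounding of OS, which is mainly use after progression. Section 5.8.1 also has patient and physician asked about subsequent treatment without repeating the exception, so loss of those data is less clear than loss of scans.

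It is tempting to add Section 5.9, which lists "Severe non-compliance to study protocol that, in the opinion of the Investigator or sponsor, warrants withdrawal; eg, refusal to adhere to scheduled visits" among grounds for leaving the study. That rule is permissive, and deleting it would not obtain scans from a patient who refuses visits, so it forms no part of this point.

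Finally, the synopsis says the endpoints had been met by Amendment 07. New wording cannot recover past scans. The text still stands, however, and Section 9.5.1 has progression-free patients scanned every 26 weeks with scans sent to BICR.

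**Conclusion.** The contradiction is real and lies in operative text for a co-primary endpoint. If sites followed the exception, patients joining another trial before BICR progression would lose scans and questionnaires, and later the second-progression checks. Their PFS would be censored at the last RECIST assessment unless death came before two missed visits. That censoring may be informative, and the planned sensitivity analysis would not undo it. OS follow-up is unaffected.

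The size and direction cannot be stated without a by-arm count of such patients, which the documents do not give. The stated design power is reproduced. The figures in steps 5 and 6 of the working rest on assumed loss rates and are not estimates of effect.

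The 6.4.9 mismatch is secondary: it is a genuine inconsistency with no shown effect on PFS.

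**What to change.** In Section 5.8.1, delete the last of the three conditions, enrolment in another clinical study. State that tumour assessments to confirmed progression, and second-progression, subsequent-therapy and survival data, continue after a patient joins another study unless consent for them is withdrawn. Allow scans taken in that study to be submitted for BICR.

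Reconcile Section 6.4.9 with Sections 5.8 and 13.3.1, so that stopping drug and leaving the study are kept apart for data collection. No clinical rule is proposed.

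The cost is amendment wording and some site effort: sites must request outside scans and dates, and some will be missing.
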